9.3 Protocol Violations

A protocol violation occurs when the participant, study coordinator or the investigator fails to adhere

to significant protocol requirements affecting the inclusion, exclusion, participant safety and primary endpoint criteria. Protocol violations for this study include, but are not limited to, the following:

1. Use of a prohibited concomitant medication
2. Non-compliance with study drug regimen

Failure to comply with Good Clinical Practice (GCP) guidelines will also result in a protocol violation. The principal investigator in consultation with IND Sponsor will determine if a protocol violation will result in withdrawal of a participant. A listing of protocol deviations by intervention group and overall will be provided.

9.4 Demographic and Baseline Variables

Demographic variables for participants will be:

1. Age in years at consent
2. Dichotomized age (≤ 65 or > 65)
3. Sex
4. Race (American Indian / Alaska Native, Asian, Black / African American, Native Hawaiian / Other Pacific Islander, White, Unknown)
5. Ethnicity (Hispanic, non-Hispanic)
6. Height
7. Weight

Baseline variables for participants will be:

8. D-dimer
9. SpO₂ and SpO₂/FiO₂
10. COVID ordinal scale score
11. Hematology labs: C-reactive protein, LDH, ferritin, leukocyte count, and platelet count in the blood
12. Temperature
13. Glomerular filtration rate (GFR)

9.5 Concurrent Illnesses and Medical Conditions

All participants' non-study medications will be administered at the discretion of the treating medical provider. Any medications and supplements are allowed except:

- Dual antithrombotic therapy (aspirin or P2Y12 inhibitor plus anticoagulation to treat deep venous thrombosis or pulmonary embolism). Single antiplatelet agent, or anticoagulant agent at prophylaxis or therapeutic dose is permitted.
- Any medication deemed by the PI to be unsafe or likely to confound analysis.

9.6 Treatment Compliance

We will summarize participant medication exposure, including missed doses, using descriptive statistics including n, mean, median, standard deviation, minimum, and maximum. The summary will include the total number of patients on drug from Day 1 through Day 14 separately by treatment.

10 Efficacy Analyses

Continuous variables will be summarized using descriptive statistics including n, mean, median,

standard deviation, minimum, and maximum. Qualitative variables will be summarized using counts and percentages. Summaries will be provided by treatment groups and overall. Two-sided hypotheses will be tested for efficacy endpoints at the 5% level.

Unless otherwise stated, analyses will be performed on the mITT population and will be programmed in SAS software (SAS Institute, Inc., Cary, NC), while graphics will be generated using R (R Core Team, 2020).

10.1 Primary Efficacy Analysis: D-dimer

The first co-primary endpoint is mean daily change in D-dimer during up to 14 days of hospitalization. We will assess longitudinal trends in the mITT analysis set via linear mixed effects regression of log-transformed D-dimer values:

$$\log(D\text{-dimer}_{it}) = \text{Intercept}_i + \text{Slope}_i \times t$$

where i indexes the patient, and t is time since first drug administration. The intercept will consist of an overall intercept term plus terms for treatment, both stratification factors (sex and an indicator for age ≥ 65 years), baseline log(D-dimer), and a random patient effect. We will model treatment interactions by stratification factor.

The hypothesis is that patients in the treatment arm will have a smaller mean slope than those in the placebo arm. Because we are conducting an interim analysis for efficacy (Section 8.6.2.1), we adopt the O'Brien-Fleming method to partition the overall Type I error rate: $\alpha = 0.006$ for the interim analysis, and 0.022 for each primary efficacy analysis based on an interim population of $n = 45$.

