STATISTICS Primary Analysis Plan	
For analysis of the first primary endpoint, we will estimate patient-level relative change in D-dimer by fitting a random coefficients regression model to log-scale D-dimer levels. The model will include treatment effects, baseline D-dimer levels, and stratification factors (sex and age), including treatment interactions with stratification factors.
 
The hierarchical composite endpoint will be analyzed using a win ratio algorithm stratified by age and sex. In a win-ratio analysis, all treatment patients are compared pairwise to all control patients, and the patient with better outcomes ‘wins’ (as determined by the hierarchy of the composite endpoint). The algorithm results in a ranking of patients that are analyzed nonparametrically by a Mann-Whitney U test.

SAMPLE SIZE RATIONALE	
Decision thresholds and power are based on a preliminary analysis of 147 D-dimer measurements taken on 41 COVID-19 patients in the University of Michigan hospital. We used a simulation approach matching the patient population characteristics learned from the analysis of preliminary data reported above.
 
For power simulation, the intraclass correlation coefficient (ICC) was set to 0.7, somewhat lower than the observed ICC of 0.77, in order to provide a margin for uncertainty in the pilot results. Power is based on a 13% daily increase in D-dimer levels for untreated patients, as observed in preliminary analysis. We posited a 50% reduction in the growth rate for the 100 mg dose. Using 2 arms with 40 subjects per arm (80 subjects in all), power is 0.91 for comparing the pooled dipyridamole participants to the controls.
 
At the December 2020 DSMB meeting, it was decided to promote the hierarchical composite endpoint to a primary endpoint. Sample size for this analysis are calculated according to methods presented in Yosef et al. (2019).

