15.3 Analysis of Primary Endpoints

Due to changes in standard of care, the initial D-dimer endpoint may no longer be clinically meaningful. Standard care of treatment for COVID-19 has changed to include anti-inflammatory

steroids which decrease D-dimer levels. Looking for an impact of dipyridamole to further reduce already diminished D-dimer levels is of limited value. In light of the changes to standard of care, it was decided to evaluate the effect of dipyridamole on clinical outcomes more directly by elevating the hierarchical composite outcome from a secondary endpoint to a primary endpoint.

The first primary endpoint is the relative change in D-dimer level over time during up to 14 days of hospitalization. We will assess the trend across D-dimer measurements obtained every second day, but we anticipate that some patients will have fewer measures (e.g. due to discharge before day 14). Linear mixed effects regression will be used to assess the longitudinal trend in log-transformed D-dimer values. The regression model will have a fixed intercept and fixed slope for each treatment arm, and a random intercept and random slope for each subject. The model will also include treatment interactions by stratification factor (sex and age). The primary hypothesis is that the treatment arm will have a smaller fixed slope than the control arm, indicating that treated subjects' D-dimer levels either increase more slowly or decrease relative to those of the control subjects.

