Mixed effects regression makes use of all available information for each subject -- even a subject with a single D-dimer measurement can be included. This technique efficiently makes use of the partial or full data observed from each subject, implicitly weighting subjects more if they have more observed points. We note that subjects who do well and are discharged relatively earlier will be somewhat down-weighted due to having fewer measurements, but this is appropriate since our primary aim is to assess moderation of D-dimer increase in-hospital. Discharge and other outcomes are discussed below as secondary aims. We also note that this approach quantifies the change in D-dimer as a linear trend on the log scale. Our preliminary analysis of D-dimer levels in patients with COVID-19 supports this simple approach to quantifying D-dimer variation. Although D-dimer can fluctuate from day-to-day, the longer-term trend is primarily linear, but we acknowledge that some patients may exhibit other patterns of change.

The second primary endpoint is a hierarchical composite of:

- Time of death from any cause during study duration
- Number of days on mechanical ventilation during study hospitalization
- Decrease in SpO₂/FiO₂ ratio of at least 50 units relative to baseline at any time during the observation period, and
- The cumulative sum of COVID ordinal scores during study hospitalization.

The composite endpoint will be nonparametrically assessed by comparing global composite rank score outcomes²⁴ across pairs of patients and evaluating a 'win ratio' using the Mann-Whitney U statistic. Each pair consisting of one treated and one untreated subject is ranked as defined below:

1. If both subjects die, then the subject who lives longer wins.
2. If exactly one subject dies, then the subject who does not die wins.
3. If the subjects are tied after step 2 (neither subject dies), then the subject with fewer days on ventilator wins.
4. If the subjects are tied after step 3, and only one of the subjects has a decrease in SpO₂ of 50 or greater, then the subject who does not have the decrease in SpO₂ wins.

5. If the subjects are tied after step 4, then the subject with lower Ordinal score wins.
6. If the subjects are tied after step 5, then their final result is a tie

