5.2 Endpoints

For convenience, we give names to the following times and time windows:

- Baseline or Day 1: Date of the first study drug administration
- Study Hospitalization: Day 1 through either Day 14 or hospital discharge, whichever is first
- Observation Period: The 28-day period following first study drug administration
- Study Duration: The period from baseline until 30 days after last study drug administration

If an endpoint is to be evaluated at all three of the above time points, we use the phrase ‘at any time point’.

Endpoints are presented in a numbered list to facilitate references to endpoints when conducting the final analysis.

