8.4 Missing Data

We anticipate three sources of missing response data in this study: missing data entries, loss to follow-up, and early hospital discharge. We will summarize missingness for primary study endpoints. In preliminary results, a large majority of patients have early hospital discharge.

For the primary response and other longitudinal analyses, we address missing response data through random coefficients regression, which incorporates missingness through the standard errors of subject-level trend estimates. This strategy assumes missing entries are missing at random and that missing entries from early termination or discharge would not differ from the trend in the observed data. For time-to-event responses, we address early termination and discharge by right-censoring.

The DICER team will review data to minimize missingness in sex, age, and baseline values. Following Schafer et al. (1997), if these variables are missing for more than 5% of patients, we will impute them using SAS PROC MI and PROC MIANALYZE if necessary. Otherwise, we will exclude missing records from the analyses.

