8.5 Extra Data

The protocol calls for certain procedures only on specified days (e.g. coagulation panels including D-dimer on Days 1, 3, 5, 7, 9, 11, 13, and 14) but allows for collection on other days when ordered by the clinician. We choose to include these ad hoc data in all analyses, because the frequency of sampling the time scale of change in response variables is anticipated to be long compared to sampling, and clinician-ordered sampling should not introduce sizeable bias.

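### SAP 10.1 makes baseline log D-dimer a covariate without removing Day 1 from the response; used both ways, it distorts the slope standard error and, with early discharge, costs power

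*SAP*

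**What the plan says.** SAP 10.1 gives each patient an intercept and a slope for log D-dimer over time since first dose. The intercept holds treatment, sex, age group, "baseline log(D-dimer), and a random patient effect". The protocol synopsis also lists baseline D-dimer among the model terms.

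SAP 5.2 defines "Baseline or Day 1: Date of the first study drug administration". SAP 8.5 lists "coagulation panels including D-dimer on Days 1, 3, 5, 7, 9, 11, 13, and 14", so the baseline value is also the first scheduled value in the series. Neither document takes it out of the response. Protocol 15.3 adds that "even a subject with a single D-dimer measurement can be included".

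On random effects, Protocol 15.3 specifies "a random intercept and random slope for each subject", and SAP 8.4 says "we address missing response data through random coefficients regression". The SAP 10.1 formula has a patient-indexed slope, but its text names a random effect only in the intercept.

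On length of stay, SAP 8.4 reports: "In preliminary results, a large majority of patients have early hospital discharge". SAP 8.6.2.1 says that most patients have gone home by Day 7.

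**The concern.** A programmer who follows SAP 10.1 literally would put the Day 1 value on both sides of the equation. At time zero the covariate then predicts the response almost perfectly. Every later value keeps its own noise and also carries the noise of the Day 1 value through the covariate. This is a step between Day 1 and all later days. A random intercept and slope with one residual variance cannot describe such a step, so the fit absorbs it as slope variation that does not exist.

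The treatment-by-time term is the first co-primary test. A wrong standard error there affects its error rate and its chance of detecting a real effect. Short stays make this worse, because few later values remain to separate the step from a slope.

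**Working it through.** **1. Inputs from the documents.** Growth of 13% per day untreated and 6.5% on drug, ICC 0.7, 40 per arm and power 0.91 (SAP 7.1). Within- and between-patient variation of about 90% and 300%, and up to 7 measurements (Protocol 15.6). Enrolment halted at 100 (Protocol synopsis). Two-sided alpha 0.022 for the final test (SAP 10.1).

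**2. The plan's own figure.** The slope difference is ln(1.13) − ln(1.065) = 0.0592. Read 90% and 300% as fold changes of 1.9 and 4, and impose ICC 0.7: within-patient SD = √[0.3 × (ln²1.9 + ln²4)] = √[0.3 × (0.412 + 1.922)] = 0.837. Seven values at times 0, 2, …, 12 have sum of squares 112, so the SD of a patient's slope is 0.837/√112 = 0.0791. The standard error of the difference is 0.0791 × √(2/40) = 0.0177. Then z = 0.0592/0.0177 = 3.35, and power at two-sided 0.05 is Φ(3.35 − 1.96) ≈ 0.918, close to 0.91. Other readings of the two percentages, with 7 or 8 values, give 0.81 to above 0.99, so the match depends on this reading. It also assumes complete follow-up and no true slope variation.

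**3. Assumptions for the simulations.** The documents do not give the discharge pattern, the log-scale SDs or the slope SD. Assumed: within-patient SD 0.64 or 0.84, true slope SD 0 to 0.10, discharge unrelated to D-dimer, no treatment-by-stratum terms. One set used fixed distributions of 1 to 8 measurements per patient. The shares with nothing after Day 7 (at most 4 measurements) were:
- mild: 5 + 15 + 20 + 20 = 60%
- early: 10 + 25 + 25 + 17 = 77%
- very early: 15 + 35 + 25 + 12 = 87%

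The other set used stays of 1 day plus an exponential time with mean 5 or 8 days, leaving 30% or 47% in hospital after Day 7. All fits were REML, with 100 patients unless stated and 160 to 800 runs per setting.

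**4. Random intercept and slope, double use.** The random-intercept variance collapses towards zero, and the slope variance is estimated at 0.014 when the truth is 0. The mean standard error is 1.12 to 1.27 times the true sampling SD. Type I error is 0.000 to 0.016 at nominal 0.022. Power at 0.022:

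| Setting | Double use | Day 1 as response only | Relative loss |
|---|---|---|---|
| Full 14 days, 80 patients | 0.90 | 0.94 | 4% |
| Mild early discharge | 0.30 | 0.50 | 40% |
| Early, slope SD 0 | 0.126 | 0.276 | 54% |
| Early, slope SD 0.10 | 0.136 | 0.192 | 29% |
| Early, slope SD 0, independent random effects | 0.074 | 0.288 | 74% |
| Nothing after Day 7 | 0.07 | 0.14 | about 50% |
| Very early | 0.08 | 0.32 | 75% |
| Exponential stay, mean 5 | 0.10 | 0.24 | 58% |
| Exponential stay, mean 8 | 0.38 | 0.45 | 16% |

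The last two rows used 160 runs. The Monte Carlo error of 0.45 is √(0.45 × 0.55/160) = 0.04, so the low end of the range is approximate. Larger runs with mean stay 8 gave 0.40 against 0.59 (slope SD 0.05, loss 32%) and 0.26 against 0.38 (slope SD 0.08, loss 32%).

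**5. Random intercept only.** With true slope SD 0, double use gives a standard error of 0.84 to 0.95 of the true SD, and type I error of 0.05 to 0.12 at nominal 0.05. When slopes truly vary, most of the error comes from omitting the random slope. In the early pattern with slope SD 0.10 the ratio is 0.52 with double use and 0.61 without, and type I error at nominal 0.022 is 0.232 and 0.156.

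**6. Candidate remedies.** Four exponential settings: slope SD 0.05 with mean stay 5 and 8, then slope SD 0.08 with mean stay 5 and 8. A common Day 1 mean gives power 0.42, 0.61, 0.27, 0.41, against 0.35, 0.59, 0.24, 0.38 for Day 1 as response only. In a repeat of these settings (200 runs each), keeping the covariate and dropping the Day 1 row gives 0.17, 0.39, 0.14, 0.25. Double use there gives 0.12, 0.41, 0.09, 0.26, and response only 0.33, 0.53, 0.20, 0.35. On full data, dropping the row gives 0.78, below the 0.90 for double use.

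**The case against.** The strongest objection is that no sentence says Day 1 is a response in the covariate model. The single-measurement remark describes the Protocol 15.3 model, which lists no baseline covariate. SAP 8.4 allows imputation of missing baselines, so a lone post-baseline value could also enter. This stands as a limit: double use is an inference from what the SAP leaves in place. It does not remove the point, because the text as written leads to that model.

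A reader might infer that the standard error is simply too large. The documents do not support that without qualification. Protocol 15.3, SAP 8.4 and the formula in 10.1 favour a random slope, but the 10.1 text names only a random effect in the intercept, and under that reading the direction reverses.

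A reader might also infer that double use accounts for the fall from 0.91. It does not. In the early-discharge settings above, the model with Day 1 as response only has power of about 0.14 to 0.59, so early discharge does most of the damage.

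Finally, a conservative test cannot create a false positive, the protocol itself doubts that D-dimer is still clinically meaningful, and recruitment stopped for futility. These points limit the urgency. D-dimer nevertheless remains a co-primary endpoint with its own 0.022.

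**Conclusion.** The point holds in conditional form. If SAP 10.1 is followed as written, Day 1 log D-dimer is most naturally used twice, and the standard error of the treatment-by-time term is then wrong under either reading of the random effects. With a random intercept and slope it is about 1.1 to 1.3 times too large and the test is conservative. With a random intercept only it is too small and type I error is inflated.

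Under the likelier random-slope reading, the relative power loss at 0.022 is about 15% to 75% when most patients leave early, and about 4% or less with full follow-up. The size depends on the assumed discharge pattern, log-scale SDs, slope SD and random-effects covariance, none of which the documents give. It is measured against power already well below 0.91. The change should be made, since the better model uses the same data.

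**What to change.** In SAP 10.1:
- State that all log D-dimer values from Day 1 onward are responses, and delete the baseline log D-dimer covariate.
- Preferably give both arms a common Day 1 mean (no treatment term at time zero). Randomisation justifies this for samples drawn before the first dose. SAP 5.2 defines Day 1 by date only, so say which Day 1 sample counts.
- State that a random intercept and a random slope are fitted for each patient, and name their covariance structure.

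Make the protocol synopsis match, exempt these models from the general baseline-covariate sentence in SAP 8.3, and apply the same rule to the change-over-time models in SAP 10.4 and Protocol 15.5, which borrow this method.

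Do not offer the alternative of keeping the covariate and dropping the Day 1 row as equivalent. It largely corrects the standard error but restores little power, and it excludes patients with only a Day 1 value, contrary to Protocol 15.3.

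The cost is a sentence or two of SAP text and one model statement. No new data are needed.

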10.2 Primary Efficacy Analysis: Hierarchical Composite Endpoint

The second co-primary endpoint is a hierarchical composite endpoint of death, survival, mechanical ventilation, SpO₂/FiO₂, and cumulative COVID ordinal scores. With one exception, the analysis of the mITT population will be identical to the interim analysis described in Section 8.6.2.2 based off the win ratio algorithm described in Section 9.2.1. The interim analysis was pooled across stratification factors (age and sex). The primary efficacy analysis will stratify win-ratio calculations by age and sex and estimate an overall win ratio across strata (Dong et al., 2018).

The hypothesis is that patients in the treatment arm will experience better outcomes than patients in the placebo arm, leading to a win proportion significantly higher than 0.5. Because we are conducting an interim analysis for efficacy (Section 8.6.2.1), we adopt the O'Brien-Fleming method to partition the overall Type I error rate: $\alpha = 0.006$ for the interim analysis, and 0.022 for each primary efficacy analysis based on an interim population of $n = 40$.

10.3 Secondary Efficacy Analyses

We will conduct secondary analyses on each component of the hierarchical composite endpoint:

- Time to death
 - *Analysis:* Cox proportional hazards regression
- Number of days on mechanical ventilation during study hospitalization
 - *Analysis:* Negative binomial regression
- Dichotomized (yes/no) decrease in SpO₂/FiO₂ ratio of at least 50 units relative to baseline at any time during the observation period
 - *Analysis:* Logistic regression

- Cumulative sum of COVID ordinal scores during study hospitalization
 - *Analysis:* Mann-Whitney U-test (nonparametric)

We will analyze an additional secondary endpoint:

- Days alive and free of organ support, where organ support is defined as receipt of invasive mechanical ventilation, vasopressor therapy, ECMO support, or incident dialysis
 - *Analysis:* Mann-Whitney U-Test (nonparametric)

Each analysis will include interactions of the study drug by stratification factor.

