3.2 Secondary Outcomes

1. **Title:** Data

Description: Days to mortality.

Time Frame: Data gathered through 28 ± 1 day

2. **Title:** Mechanical ventilation days
Description: Days spent on mechanical ventilation.
Time Frame: Data gathered through 28 ± 1 day
3. **Title:** Change in SpO₂/FiO₂
Description: Dichotomized outcome of decrease in daily average SpO₂/FiO₂ of 50 or greater compared to enrollment SpO₂/FiO₂.
Time Frame: Data gathered through day 14
4. **Title:** Cumulative sum of Ordinal scores
Description: Sum of daily Ordinal scores during hospitalization. This is a rough approximation of duration and severity.
Time Frame: Data gathered through day 14
5. **Title:** Days alive and free of organ support
Description: Organ support is defined as receipt of invasive or non-invasive mechanical ventilation, high flow nasal oxygen, vasopressor therapy, ECMO support, or dialysis.
Time Frame: Data gathered through day 14

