- $CP \geq 0.9$: Stop study for benefit
- $0.8 \leq CP < 0.9$: Continue study to planned $N = 127$
- $0.3 \leq CP < 0.8$: Continue study to with re-estimated sample size not to exceed 160
- $CP < 0.3$: Stop study for futility

15.4 *Analysis of Secondary Endpoints*

We will conduct secondary analyses on each component of the hierarchical composite endpoint:

- Time to death
 - *Analysis:* Cox proportional hazards regression
- Number of days on mechanical ventilation during study hospitalization
 - *Analysis:* Poisson regression with subject-level random effects
- Dichotomized (yes/no) decrease in $\text{SpO}_2/\text{FiO}_2$ ratio of at least 50 units relative to baseline at any time during the observation period
 - *Analysis:* Logistic regression
- Cumulative sum of COVID ordinal scores during study hospitalization
 - *Analysis:* Mann-Whitney U-test (nonparametric)

We will analyze an additional secondary endpoint:

- Days free of organ support, where organ support is defined as receipt of invasive or non-invasive mechanical ventilation, high flow nasal oxygen, vasopressor therapy, ECMO support, or COVID-related dialysis, and
- Death at any time is assigned a value of 0 days.
 - *Analysis:* Mann-Whitney U-Test (nonparametric)

Each analysis will include interactions of the study drug by stratification factor.

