6.4.10 Modified WHO COVID-19 8-point Ordinal scale assessment

Ordinal scale assessments will be made daily and on Day 28 as below:

Table 2. Modified COVID 8-Point Ordinal Scale

Patient State	Descriptor	COVID Ordinal Score
Dead	Death	8
Hospitalized – severe disease	Ventilation + additional organ support (pressors, renal replacement therapy, ECMO)	7
	Intubation and mechanical ventilation	6
	Non-invasive ventilation or high-flow oxygen	5
Hospitalized – mild disease	Oxygen by mask or nasal prongs	4
	Hospitalized, no oxygen therapy	3
Ambulatory	Limitation of activities	2
	No limitation of activities	1

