
[1] Death and survival are assessed from the time of study medication to 30 days after the last dose of study drug (a maximum of 44 days from consent). Participants are censored at the time of drop-out or the data cutoff date (if no event has occurred).
 
[2] Number of days on mechanical ventilation are counted from the time of study medication until hospital discharge. If a participant is re-hospitalized and receives ventilation, these data are not counted.
 
[3] Oxygenation measurements are collected from EHR records. Baseline is defined as the average of measurements taken between 8 hours prior to start of study medication and the start of study medication administration. A 50-point drop is defined as a participant who experiences two consecutive measures of at least 50 points below baseline. Post-baseline measurements are assessed up to and including day 44 (from consent).
 
[4] COVID ordinal scores are defined in Table 2.
						

The cumulative sum of COVID ordinal scores used in Step 6 is calculated as the time-weighted sum of daily ordinal scores, with units of ordinal score days. For example, if a subject started medication at 9:00 pm on Day 1 with a score of 4, and that score decreased to 3 at 6:00 am the next day, and that patient was discharged at noon on the third day, then the cumulative sum of ordinal scores would be:

$$\frac{\{3 \text{ hrs} \times 4 + (6 \text{ hrs} \times 4 + 18 \text{ hrs} \times 3) + 12 \text{ hrs} \times 3\}}{24 \text{ hrs/day}} = \frac{12 + (24 + 54) + 36}{24} = 5.25$$

The use of the cumulative ordinal score in Step 6 of the above algorithm is meant as a combined measure of the severity and duration of a patient's illness, since longer hospitalizations and larger daily ordinal scores will both increase the cumulative total.

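### SAP 10.3 tests the cumulative ordinal score on its own with no rule for deaths, so an early death can rank favourably and the test can hide a mortality benefit

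*SAP*

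**What the plan says.** SAP 10.3 lists each component of the hierarchical composite as a separate secondary analysis. Two matter here:

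- "Cumulative sum of COVID ordinal scores during study hospitalization", by Mann-Whitney test.
- "Dichotomized (yes/no) decrease in SpO₂/FiO₂ ratio of at least 50 units relative to baseline at any time during the observation period", by logistic regression.

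Under SAP 10, both are run in the mITT population. SAP 8.7 places them among five secondary analyses under a Bonferroni adjustment.

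Protocol 3.2 describes the first as "Sum of daily Ordinal scores during hospitalization". SAP 9.2.1 computes it as a time-weighted total, and its worked example ends at discharge. A lower total wins, because "longer hospitalizations and larger daily ordinal scores will both increase the cumulative total". SAP 5.2 sets the window: "Study Hospitalization: Day 1 through either Day 14 or hospital discharge, whichever is first". Table 2 of the SAP gives death a score of 8. SAP 9.2.1 (Table 3, note 3) counts an SpO₂/FiO₂ drop only after two consecutive readings at least 50 points below baseline.

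Neither document says what a patient who dies contributes to either stand-alone test. Death is not among the three sources of missing response data in SAP 8.4. Protocol 15.4 does have a death rule for organ-support-free days ("Death at any time is assigned a value of 0 days"), but gives none for these two endpoints. SAP 10.3 does not repeat even that rule.

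**The concern.** In the win ratio no death rule is needed for the lower tiers. Any pair with a death is decided on death or survival time, so ventilator days, the SpO₂/FiO₂ drop and the ordinal sum are compared only between two survivors (SAP 9.2.1, Table 3). Once a component is tested alone in all mITT patients, that ordering disappears.

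The ordinal sum rewards a short stay. If accrual stops at death, a short stay that ends in death is rewarded in the same way as a short stay that ends in recovery. The plan expects deaths, since 10 of them trigger a DSMB review (SAP 8.6.1). It also reports that most patients go home early (SAP 8.4), so survivors' sums are small and an early death does not stand out as bad.

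At stake is the interpretation of two of the five multiplicity-controlled secondary tests. They are components of the composite, and one or both could fail to show, or could contradict, a benefit that the composite detects through mortality.

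**Working it through.** **1. The SAP's own figure.** The worked example in SAP 9.2.1 reproduces: (3×4 + 6×4 + 18×3 + 12×3)/24 = 126/24 = 5.25. Accrual runs from first dose to leaving hospital.

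**2. Two readings of a death.**
- *Stop at death.* Protocol 3.2 limits the sum to the hospital stay, the example stops at departure, and Table 2 lists dead and hospitalized as different states.
- *Carry 8 to Day 14.* Death scores 8, and the window in SAP 5.2 ends at Day 14 or discharge without naming death.

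Death on Day 2 after score 5: 2×5 = 10 under the first reading, 10 + 12×8 = 106 under the second. The unwritten choice moves the same patient from near best to worst.

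**3. Individual patients, stopping at death.** Death after 3 days at score 6: 3×6 = 18. Discharge after 5 days at score 4: 5×4 = 20, which ranks worse. Timing matters. Assume survivor stays are lognormal with a median of 4 to 7 days and a mean score of 4.2 (the documents give no figures):

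| Death | Sum | Share of survivors it outranks |
|---|---|---|
| Day 2, score 5 | 10 | 80–96% |
| Day 3, score 5 | 15 | 57–86% |
| Day 5, score 5.5 | 27.5 | 21–54% |
| Day 10, score 6 | 60 | 1–7% |

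**4. Effect on the test.** Simulation with 50 per arm (enrollment was halted at 100, randomized 1:1). Assumed inputs: survivors stay 1 + Poisson(5) + Exp(1) days at score 3, 4 or 5 (15/60/25%); deaths occur on days 2 to 8 at score 5 to 7; the drug prevents some deaths and changes nothing else. Saved patients either spend about 14 days at score 6 or have an ordinary survivor's course. The win proportion is for the treated arm:

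| Deaths, control vs drug | Saved patients | Raw sum | Deaths ranked worst |
|---|---|---|---|
| 15% vs 5% | long ventilated stay | 0.456 | 0.510 |
| 15% vs 5% | ordinary stay | 0.504 | 0.551 |
| 20% vs 5% | long ventilated stay | 0.433 | 0.516 |
| 20% vs 5% | ordinary stay | 0.505 | 0.575 |

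Repeat runs of the raw sum agree to within about 0.005. The survivor model of step 3, with the drug halving control mortality of 10–30% and rescued patients staying to Day 14, gives 0.39–0.49 raw (median day of death from 2 to 12) and 0.50–0.53 with deaths ranked worst.

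**5. How often it would be declared harm.** The null standard error is √[(50+50+1)/(12×50×50)] = 0.058, so 0.456 is z = −0.044/0.058 ≈ −0.8 and 0.433 is z ≈ −1.2. At the Bonferroni level 0.05/5 = 0.01, significant harm occurs in about 3–8% of simulated trials with long-stay saved patients.

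**6. SpO₂/FiO₂ drop.** Let m be control mortality, s the drop rate in ordinary survivors, q the fraction of deaths with two prior qualifying readings, and r the drop rate in rescued patients. If the drug halves deaths:
- control = m·q + (1−m)·s
- drug = ½m·q + ½m·r + (1−m)·s

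With assumed m = 0.20, s = 0.30, r = 0.90:
- q = 0: 24% vs 33%
- q = 0.6: 36% vs 39%
- q = 0.9: 42% vs 42%
- q = 1: 44% vs 43%

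If r = 0.30 instead, the drug looks better once q exceeds 0.30. Counting every death as an event is the same as q = 1, which gives 44% vs 43% (r = 0.90) or 44% vs 37% (r = 0.30).

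**The case against.** A reader might infer that the plan scores early death as one of the best outcomes, so that a life-saving drug would look harmful. The documents do not support that, for four reasons.

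- They do not state the stopping rule. Carrying 8 to Day 14 is open, and under it early deaths rank very badly. What is established is a missing rule with an unfavourable natural reading.
- Even when the sum stops at death, deaths as a group rank about average in the simulation of step 4: a random death beats a random survivor 47% of the time. Only very early deaths rank among the best, and the exclusion of patients judged unlikely to survive more than 48 hours makes those less common.
- The reversal in step 4 appears only when saved patients have long ventilated stays. With ordinary stays the raw result is null. Significant harm at 0.01 is uncommon in either case.
- For SpO₂/FiO₂, many patients dying of respiratory failure may already have two qualifying readings. The bias depends on that fraction, which the documents do not give.

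It is also fair that the composite puts death first, that time to death is tested separately, and that Protocol 3.2 presents the sum only as a rough guide to duration and severity.

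All of this limits the claim without removing it. With the sum stopped at death, the raw test loses the mortality benefit in both versions of step 4, and an endpoint meant to reflect severity should not credit a patient for dying early.

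**Conclusion.** The concern holds in a limited form. SAP 10.3 has no death rule for the stand-alone ordinal sum. Under the natural reading the test can hide a mortality benefit, and could point toward harm if the patients saved have long ventilated stays. In the 15% versus 5% illustration, stopping at death costs about 0.05 on the win proportion: 0.46 against 0.51 with long stays, 0.50 against 0.55 with ordinary stays. These sizes rest on assumed lengths of stay, times of death and courses of saved patients.

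The stand-alone SpO₂/FiO₂ test has the same gap, since a death without two prior qualifying readings counts as no drop. The size and direction of that bias cannot be fixed from the documents. The co-primary composite and the time-to-death analysis are unaffected. This should be corrected before the final analysis, but it does not threaten the primary result.

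**What to change.** In SAP 10.3:

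- **Ordinal sum:** rank all deaths as the worst values, with earlier death worse, then apply the Mann-Whitney test as planned. State the death window; using the composite's own window would keep the two consistent.
- **SpO₂/FiO₂:** analyse a drop of at least 50 or death as the binary event.
- **Composite:** leave unchanged.

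Carrying score 8 to Day 14 should not be described as equivalent to worst rank. Death after 12 days at score 4 would total 48 + 2×8 = 64, still better than a survivor ventilated for 14 days at score 6 (84), and deaths after Day 14 would add nothing. A Day 3 death after 18 points would total 18 + 11×8 = 106.

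The stand-alone test of ventilator days also lacks a death rule, so the same edit could state one.

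The cost is a sentence per endpoint and a few lines of code. The data are already collected, and SAP 8.1 makes the final analysis wait for SAP approval.
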